5.5.4 Treatment Adherence

Study personnel will review the dosing compliance with subjects at each clinic visit, and make record of treatment adherence in the patient's medical record. In addition, study diaries will be provided to subjects at the beginning of each cycle of lenalidomide therapy. Subjects will be asked to record days on which lenalidomide is taken, and return the study diary at the end of each cycle. These diaries will not be mandatory, but will serve as supplemental documentation to dosing information collected during each study visit.

Any unused Revlimid® (lenalidomide) should be returned by the patient for disposition in accordance with the Revlimid REMS® program.

5.6 Concomitant Therapy

5.6.1 Recommended Concomitant Therapy

Subjects should receive full supportive care, including transfusions of blood and blood products, antibiotics, analgesics, and antiemetics when appropriate.

5.6.1.2 Anticoagulation

Lenalidomide increases the risk of thrombotic events in patients who are at high risk or with a history a thrombosis, in particular when combined with other drugs known to cause thrombosis. When lenalidomide is combined with other agents such as steroids (e.g. dexamethasone, prednisone), anthracyclines (Doxil, Adriamycin) and erythropoietin the risk of thrombosis is increased. For information on the risk of venous thromboembolism with combined oral contraception see Appendix: Risks of Fetal Exposure, Pregnancy Testing Guidelines and Acceptable Birth Control Methods.

Study subjects will use aspirin (81 or 325 mg) or some other form of prophylaxis as deemed appropriate while taking lenalidomide. Low molecular weight heparin may be utilized in patients who are intolerant of aspirin. Coumadin should be used with caution and close monitoring of INR. Patients who are intolerant of anti-coagulants due to

bleeding disorders or for whom anti-coagulation is contraindicated may participate in this study and receive daily dosing with lenalidomide with approval from the principal investigator.

If prophylactic anti-coagulation is used, it should be held for platelet counts $< 50,000/uL$, and then restarted when platelet counts are at or above this level.

5.6.2 Prohibited Concomitant Therapy

Concomitant use of sargramostim (GM-CSF), anti-cancer therapies, including radiation, thalidomide, or other investigational agents is not permitted while subjects are receiving lenalidomide therapy during the maintenance treatment phase of the study.

5.7 Discontinuation of Study Treatment

Study treatment will continue until the completion of 24 cycles of lenalidomide maintenance therapy, or the occurrence of any of the following events:

- Disease progression (See Appendix D)
- Adverse event(s) that, in the judgment of the Investigator, may cause severe or permanent harm or which rule out continuation of the treatment regimen.
- Discontinuation or interruption in lenalidomide therapy for ≥ 28 consecutive days.
- Withdrawal of consent
- Lost to follow up
- Death
- Pregnancy or a positive pregnancy test

5.8 Follow-Up

Subjects who discontinue treatment for any reason will be followed for resolution of treatment-related adverse events and survival. At treatment discontinuation, subjects will undergo a safety assessment approximately 28 days post the last dose of protocol therapy. In addition, off study evaluations per the Schedule of Assessments, Section 2, will be performed. Subjects will be followed for additional chemotherapy and progression/survival data every three months for the first three years after study discontinuation, and then yearly until death or withdrawal from study participation.

6 Adverse Events

6.1 Serious Adverse Event (SAE) Definition

A serious adverse event is one that at any dose (including overdose):

- Results in death
- Is life-threatening¹
- Requires inpatient hospitalization or prolongation of existing hospitalization
- Results in persistent or significant disability or incapacity²
- Is a congenital anomaly or birth defect
- Is an important medical event³
- Pregnancy

¹“Life-threatening” means that the subject was at immediate risk of death at the time of the serious adverse event; it does not refer to a serious adverse event that hypothetically might have caused death if it were more severe.

²“Persistent or significant disability or incapacity” means that there is a substantial disruption of a person’s ability to carry out normal life functions.

³Medical and scientific judgment should be exercised in deciding whether expedited reporting is appropriate in situations where none of the outcomes listed above occurred. Important medical events that may not be immediately life-threatening or result in death or hospitalization but may jeopardize the patient or may require intervention to prevent one of the other outcomes listed in the definition above should also usually be considered serious. Examples of such events include allergic bronchospasm requiring intensive treatment in an emergency room or at home, blood dyscrasias or convulsions that do not result in inpatient hospitalization, or the development of drug dependency or drug abuse. A new diagnosis of cancer during the course of a treatment should be considered as medically important.

6.2 Adverse Event Reporting

The adverse event recording and reporting period will begin with each subject’s first dose of lenalidomide and will end twenty-eight days after each patient’s last dose of lenalidomide, or upon resolution of any treatment-related adverse events, should their duration extend beyond the 28-day reporting period. Pre-existing conditions (those events existing prior to each patient’s first dose of lenalidomide) will not be reported as adverse events unless they worsen in grade or severity.

Toxicity will be scored using CTCAE Version 4.0 for toxicity and adverse event reporting. A copy of the CTCAE Version 4.0 can be downloaded from the CTEP homepage ([HTTP://CTEP.INFO.NIH.GOV](http://CTEP.INFO.NIH.GOV)). All appropriate treatment areas should have access to a copy of the CTCAE Version 4.0. All adverse clinical experiences, whether observed by the investigator or reported by the patient, must be recorded, with details about the duration and intensity of each episode, the action taken with respect to the test drug, and the patient’s outcome. The investigator must evaluate each adverse experience for its relationship to the test drug and for its seriousness.

The investigator must appraise all abnormal laboratory results for their clinical significance. If any abnormal laboratory result is considered clinically significant, the investigator must provide details about the action taken with respect to the test drug and about the patient's outcome on the adverse event CRF. Lab abnormalities graded \leq grade 2 in severity will not be reported as adverse events, unless deemed to be clinically significant by the treating physician.

Lymphopenia of any grade will not be considered an adverse event.

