⁴ Progression will be determined by the treating physician as based on clinical picture and radiographic findings. The initial imaging will be performed after ASCT, but prior to initiating maintenance lenalidomide therapy. During the maintenance phase, imaging (PET/CT or CT scan) will be performed every 3 months during the first year and every 4 months during the second year of maintenance. Imaging studies after the second year of maintenance will be at discretion of treating physician. During the first cycle of maintenance therapy, there will be two visits with physical exam. Then, participants will be seen on day 1 of each subsequent cycle. It will not be required to document progression by tissue biopsy (it will be at discretion of treating physician).

⁵ An additional safety assessment will be done 28 days (+/- 7 days) following the last dose of protocol therapy.

⁶ If screening assessments were done within 7 days of Day 1, they do not need to be repeated at Study Day 1.

⁷ Lenalidomide must be prescribed through and in compliance with Celgene's Revlimid REMS® program. Prescriptions must be filled within 14 days, unless the patient is a female of childbearing potential, in which case the prescription must be filled within 7 days. Consideration should be given to prescribing lenalidomide 5 to 7 days in advance of Day 1 of each cycle to allow time for required patient and prescriber surveys, and drug shipment to patient. Any unused Revlimid® (lenalidomide) should be returned to the patient for disposition in accordance with the Revlimid REMS® program.

⁸ Subjects will be followed every 3 months for the first 3 years after discontinuation of protocol therapy, and then annually thereafter; those patients who did not achieve hematological recovery by Day 100 after ASCT and never started on lenalidomide maintenance will also be followed every 3 months for the first year and then annually for anti-cancer treatment and progression/survival information.

3 Background and Rationale

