4.1 Objectives

4.1.1 Primary Objectives

- Determine the safety and dose-limiting toxicity of lenalidomide maintenance therapy implemented early after ASCT and the appropriate dose for further studies.

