5.3.6 Study Discontinuation

The following will be performed at the time of study discontinuation, whether due to study completion or early withdrawal from study participation

- Physical Exam and evaluation of ECOG PS
- Vital signs (Blood pressure, heart rate, temperature, weight)
- CBC with differential and platelets
- Serum chemistry panel including sodium, potassium, chloride, CO₂, calcium, serum creatinine, BUN, total bilirubin, alkaline phosphatase, AST, ALT and TSH
- Assessment of adverse events and concomitant medications

5.3.7 Safety Assessment (to be performed 28 Days (+/- 7 days) after study discontinuation)

- Assessment of adverse events and concomitant medications

5.3.8 Follow-Up (to be performed every 3 months for the first 3 years after study discontinuation, and then yearly thereafter)

- Review of anti-cancer treatments
- Review of progression and survival information

Assessments to be performed at screening and during scheduled study visits are also outlined in Section 2 Table of Study Assessments.

At treatment discontinuation, subjects will undergo off study evaluations per the Schedule of Assessments, Section 2. In addition, a safety assessment will be done approximately 28 days after the last dose of protocol therapy. Follow-up contact with the subjects should occur at a minimum of 3 months during the first 3 years after finishing maintenance phase and annually after that.

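### New primary cancers that arise more than 28 days after the last dose are not actively collected, although the planned follow-up contacts could ask about them at little cost.

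*Combined protocol and SAP*

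**What the plan says.** Section 6.2 starts adverse event recording with a subject's "first dose of lenalidomide and will end twenty-eight days after each" patient's last dose. The one extension is "or upon resolution of any treatment-related adverse events, should their duration extend beyond the 28-day reporting period". The Section 2 footnotes place the last scheduled safety visit at the same point: "An additional safety assessment will be done 28 days (+/- 7 days) following the last dose of protocol therapy".

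Section 6.1 singles out new cancers: "A new diagnosis of cancer during the course of a treatment should be considered as medically important".

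Section 5.8 keeps patients in contact "every three months for the first three years after study discontinuation, and then yearly until death or withdrawal from study participation". Section 5.3.8 lists two items for those contacts: "Review of anti-cancer treatments" and "Review of progression and survival information". The follow-up column in Section 2 has the same two. Section 5.8 also follows treatment-related adverse events to resolution.

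The primary objective in 4.1.1 is to "Determine the safety and dose-limiting toxicity of lenalidomide maintenance therapy implemented early after ASCT and the appropriate dose for further studies". Section 10.6 grades and tables all observed toxicities. Section 9.1 promises a later report of the data that follow the 12-month analysis.

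**The concern.** The protocol treats other cancers as relevant. It requires patients to have been free of most other malignancies for at least 2 years (inclusion criterion 6), and it names a new cancer on treatment as an important medical event. Once the 28 days are over, no scheduled contact asks about one, although the same patients are still being contacted.

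Two things are at stake. First, the toxicity tables and the follow-up report can show a late new cancer only if it comes to light by chance. Second, a non-fatal new cancer could be scored as lymphoma progression. Under the Section 2 footnotes, progression is the treating physician's judgement and needs no biopsy, and Appendix C counts a new lesion above the stated size as progressive disease. After the window closes, no item prompts anyone to separate the two.

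**Working it through.** The plan states no figure on this point, so there is none to reproduce. The check compares the recording window with the contact period, then sizes the gap under assumed rates.

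**Inputs.** Cycle of 28 days and at most 24 cycles (5.1); recording to 28 days after the last dose (6.2); quarterly contact for 3 years after treatment (5.8), taken as 3 × 365.25 = 1,096 days; 24 evaluable patients (10.7); accrual over 36 months and a total duration of up to 60 months (10.8).

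**Step 1: windows.** Recording window = cycles × 28 + 28. Time to the end of quarterly contact = cycles × 28 + 1,096.

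| Cycles received | Recording window (days) | To end of quarterly contact (days) | Share covered |
|---|---|---|---|
| 3 | 84 + 28 = 112 | 1,180 | 9.5% |
| 12 | 336 + 28 = 364 | 1,432 | 25% |
| 24 | 672 + 28 = 700 | 1,768 | 40% |

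In every row 1,096 − 28 = 1,068 days of quarterly contact lie outside the window. Yearly contact comes on top.

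**Step 2: person-time outside the window.**
- If all 24 patients stay in contact for 3 years: 24 × 1,068 / 365.25 = about 70 patient-years. Deaths and withdrawals reduce this.
- If contact ends at 60 months (1,826 days), accrual is uniform (mean entry at 18 months, 548 days) and all patients complete 24 cycles: 1,826 − 548 − 700 = 578 days per patient on average, and 24 × 578 / 365.25 = about 38 patient-years. The last patient enrolled, at day 1,096, would have 1,826 − 1,096 − 700 = 30 days.

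**Step 3: expected cases.** The documents give no rate of new cancers, so these rates are assumptions. Expected cases = rate × person-time; chance of at least one = 1 − exp(−expected).

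| Assumed rate per patient-year | 70 patient-years: expected (chance of ≥1) | 38 patient-years: expected (chance of ≥1) |
|---|---|---|
| 0.5% | 0.35 (30%) | 0.19 (17%) |
| 1% | 0.7 (50%) | 0.38 (32%) |
| 2% | 1.4 (75%) | 0.76 (53%) |
| 3% | 2.1 (88%) | 1.14 (68%) |

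**Step 4: which results can be touched.**
- Dose-limiting toxicity is confined to the first 28 days of therapy (10.3), and the dose decision (10.4) and termination rule (10.5) use only those events. None can change.
- PFS and OS count death from any cause (10.3), so a death from a new cancer is correctly an event in both. Starting another anti-cancer treatment is neither an event nor a censoring reason in 10.3.
- A non-fatal new cancer scored as progression would be a false PFS event. PFS runs from transplant, and maintenance starts 28 to 100 days later. For a patient who stops after 3 cycles, recording ends 28 + 112 = 140 to 100 + 112 = 212 days after transplant, before the 12-month point. For a completer it ends well after 12 months. PFS at 12 months is therefore exposed only through patients who stop early without progression.

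**The case against.** The strongest reply is that nothing in the plan is wrong. Section 6.1 speaks only of cancers during treatment, and those fall inside the 6.2 window. Section 10.2 gives the primary objective as dose-limiting toxicity, which a late cancer cannot affect. New cancers are not among the adverse events listed in 3.2, and no rate is given. With 24 patients, no control arm and prior high-dose chemotherapy, one or two cases could hardly be attributed to lenalidomide. All of this stands. It limits the point to a suggested improvement and rules out any claim about a rate.

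A second reply is that other routes exist. Section 6.3.1 requires a report of any serious event within 24 hours of awareness and sets no end date of its own. Section 6.3.2 has the safety committee accept reports until 90 days after the last subject's last dose, and it lets the Medical Monitor recommend reporting of events not reported before. The review of anti-cancer treatments may also reveal a case. This stands in part: a late cancer may surface. But none of these routes requires anyone to ask, and the committee clause refers back to 6.2 for the recording period.

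A reader might also infer that the case report form cannot separate treatment for a new cancer from treatment for lymphoma. The forms are not in the documents, so one can say only that the protocol lists no such item.

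**Conclusion.** The point holds as a gap in collection. After 28 days from the last dose, no planned contact asks about new primary cancers, and no other section closes the gap. What is incomplete is the broader safety description: the toxicity tables under 10.6 and the follow-up report under 9.1. There is also a small risk that a non-fatal new cancer is counted as lymphoma progression.

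Three stronger readings are tempting, and the documents do not support them. Sections 6.1 and 6.2 do not contradict each other, because cancers on treatment are captured. The primary endpoint and the choice of dose are not compromised, because both rest on the first 28 days. Deaths from a new cancer do not distort PFS or OS, because death from any cause is an event in each; only the cause goes unrecorded.

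The size is modest. Over the three years of quarterly contact, at most about two cases are expected even at the highest assumed rate with full follow-up, and about one if the 60-month duration binds and all patients complete treatment. The rates are assumptions, and no rate could be estimated precisely from this trial. The case for change is that individual cases should be visible and that the contacts already take place. It is a cheap improvement, not the correction of an error.

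**What to change.** - Section 2 (follow-up column) and 5.3.8: add an item for new primary malignancy, with type and date.
- Section 6.2: state that new primary malignancies are recorded to the end of follow-up, whatever their attribution, as an exception to the 28-day limit. Say whether the 90-day cut-off for committee reports in 6.3.2 still applies to them.
- Section 10.6: list the cases descriptively, with person-time, for all treated patients, and make no inferential claim.

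The cost is one question at contacts that already take place, one data item, and a few more reports during follow-up. Sample size, endpoints and analysis populations do not change. The item would prompt the distinction between a new cancer and lymphoma progression but cannot guarantee it.

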6.2.1 Pregnancies

Pregnancies and suspected pregnancies (including a positive pregnancy test regardless of age or disease state) of a female subject occurring while the subject is on lenalidomide, or within 28 days of the subject's last dose of lenalidomide, are considered immediately reportable events. Lenalidomide is to be discontinued immediately. The pregnancy, suspected pregnancy, or positive pregnancy test must be reported to Celgene Drug Safety immediately by facsimile or email using the Pregnancy Initial Report Form. The female subject should be referred to an obstetrician-gynecologist, preferably one experienced in reproductive toxicity for further evaluation and counseling.

The Investigator will follow the female subject until completion of the pregnancy, and must notify Celgene Drug Safety immediately about the outcome of the pregnancy (either normal or abnormal outcome) using the Pregnancy Follow-up Report Form. If the outcome of the pregnancy was abnormal (e.g., spontaneous or therapeutic abortion), the Investigator should report the abnormal outcome as an AE. If the abnormal outcome meets any of the serious criteria, it must be reported as an SAE to Celgene Drug Safety immediately by facsimile, or other appropriate method, within 24 hours of the Investigator's knowledge of the event using the SAE Report Form.

All neonatal deaths that occur within 28 days of birth should be reported, without regard to causality, as SAEs. In addition, any infant death after 28 days that the Investigator suspects is related to the in utero exposure to the IP should also be reported to Celgene Drug Safety immediately by facsimile, or other appropriate method, within 24 hours of the Investigator's knowledge of the event using the SAE Report Form.

If a female partner of a male subject taking investigational product becomes pregnant, the male subject taking lenalidomide should notify the Investigator, and the pregnant female partner should be advised to call their healthcare provider immediately.

6.2.2 Celgene Drug Safety Contact Information:

Celgene Corporation
Attn: Medical Affairs Operations
[name]
[name]
[name]

[contact]
E-mail: [contact]

6.3 Investigator Reporting Responsibilities

6.3.1 Expedited reporting by investigator to Celgene

Serious adverse events (SAE) are defined above. The investigator must inform Celgene in writing using a Celgene SAE form or MEDWATCH 3500 form of any SAE within 24 hours of being aware of the event. The written report must be completed and supplied to Celgene by facsimile within 24 hours/1 business day. The initial report must be as complete as possible, including an assessment of the causal relationship between the event and the investigational product(s), if available. Information not available at the time of the initial report (e.g., an end date for the adverse event or laboratory values received after the report) must be documented on a follow-up report. A final report to document resolution of the SAE is required. The Celgene tracking number (RV-NHL-PI-0623) and the institutional protocol number should be included on SAE reports (or on the fax cover letter) sent to Celgene. A copy of the fax transmission confirmation of the SAE report to Celgene should be attached to the SAE and retained with the patient records.

6.3.2 Report of Adverse Events to the Institutional Review Board/Data Safety Monitoring Committee

Institutional Review Board:

Serious adverse events which in the opinion of the principal investigator are **both** unexpected **and** related to research procedures should be reported to the IRB within 10 working days of investigator notification. An event is considered “unexpected” when its specificity and severity are not accurately reflected in the protocol-related documents, such as the IRB-approved research protocol, any applicable investigator brochure, applicable package insert information, and/or the current IRB-approved informed consent document. An event is considered “related to the research procedures” if the event is deemed probably or definitely related.

Deaths occurring for patients on-study and within 30 days of study drug administration that are considered unforeseen and indicates participants or others are at increased risk of harm (i.e. unexpected and probably/definitely related), must be reported to the IRB within 24 hours of notification.

In addition, if other information becomes available that indicates a change to the risks or potential benefits of the research, in terms of severity or frequency, this should be reported within 3 days. Examples of this include:

- An interim analysis indicates that participants have a lower rate of response to treatment than initially expected.
- Safety monitoring indicates that a particular side effect is more severe, or more frequent than initially expected.
- A paper is published from another study that shows that an arm of your research study is of no therapeutic value.
- Any adverse event that represents a serious, unexpected problem that is rare in absence of drug exposure.
- Withdrawal from marketing for safety of a drug, device, or biologic used in a research protocol.
- Change to the protocol taken without prior IRB review to eliminate apparent immediate hazard to a research participant.
- Violation, meaning an accidental or unintentional change to the IRB approved protocol that placed one or more participants at increased risk, or has potential to occur again.
- Breach of confidentiality.

The IRB will accept other reports when the investigator is unsure whether the event should be reported, and the IRB will review such reports to determine whether the event meets the threshold for an unanticipated event presenting risk to the participant.

Office of Regulatory Affairs, Institutional Review Board
[name]
[contact]
[contact]

Abramson Cancer Center Data Safety Monitoring Committee (DSMC):

Grade 3 or higher AEs for Penn Subjects, determined to be related to the study drug regardless of expectedness, must be submitted to the Abramson Cancer Center's DSMC within 10 days of notification. Other events should be submitted if they may affect subject safety, if they are determined to be clinically significant, or if a relationship to the study drug cannot be ruled out. All unexpected deaths or deaths related to the study drug should be reported within 24 hours of notification. All other deaths should be reported within 30 days. Onsite SAE reports should be sent to the DSMC for 90 days following the last date the last subject received study drug, and will not be accepted or processed after that time. The AE recording period for this protocol is defined above in Section 6.2.

The following events do not require reporting to the ACC DSMC. The treating investigator must clearly document the relationship of these events.

- Grade 3 or 4 events that are probably or definitely related to the subjects' underlying disease and/or other co-morbidity.
- Grade 3 or 4 events that are probably or definitely related to an FDA approved drug based on the current labeling. However if the toxicity is more severe or is occurring more frequently than the current labeling, the event would be reportable. If the drug is not being used in accordance with the current FDA approval (i.e. dose, disease, route) then standard reporting is required.
- Grade 3 or 4 events that are obviously unrelated to the study drug (i.e. events related to a standard of care test/procedure).

AEs will be submitted to the DSMC through the Velos Clinical Trial Management System.

Medical Monitor:

The medical monitor for this study will be [name] from the University of Pennsylvania. [name] is an Assistant Professor in the Department of Hematology-Oncology at Penn, with extensive oncology and research experience. [name] has served as the Principal Investigator and as a Sub-Investigator on various other Oncology Studies at Penn. [name] is not directly involved in the trial and is not collaborating with the sponsor-investigator on any other trials.

In the role, [name] will review all AEs including grading, toxicity assignments, all other safety data and activity data observed in the ongoing clinical trial. This will include a real-time review of safety data in the event of any unexpected/related SAE regardless of grade, and any on-study deaths. The Medical Monitor will also be consulted in the case of exception requests or the evaluation of deviations that may compromise subject safety or disrupt the design of the study. This information will be communicated to the Medical Monitor via email and filed in the Regulatory Binder/Subject Chart appropriately. As applicable, copies of this correspondence will be included in the corresponding IRB/ACC DSMC submission of these events.

The Medical Monitor will also be asked to review study data and comprehensive adverse event data at least bi-annually (every 6 months) or more frequently depending on enrollment. This meeting will take place in person, and all study/safety information will be presented appropriately. This meeting will be clearly documented on a Medical Monitor Review Sheet, signed off on by the Medical Monitor. At any point during the course of the study, the Medical Monitor may recommend reporting of adverse events and relevant safety data not previously reported and may recommend suspension or termination of the trial.

